### 2.1.3 Recruitment Strategies

This protocol may be abstracted into a plain language announcement posted on NIH websites and on NIH social media platforms. Participants will be recruited from the current patient population at NIH.

## 2.2 SCREENING EVALUATION

### 2.2.1 Screening activities performed prior to obtaining informed consent

Minimal risk activities that may be performed before the subject has signed a consent include the following:

- Email, written, in person or telephone communications with prospective subjects.
- Review of existing medical records to include H&P, laboratory studies, etc.
- Review of existing MRI, x-ray, or CT images.
- Review of existing photographs or videos.
- Review of existing pathology specimens/reports from a specimen obtained for diagnostic purposes.

A waiver of consent for these activities has been requested in Section **9.6.1**.

### 2.2.2 Screening activities performed after a consent for screening has been signed

The following activities will be performed only after the subject has signed the consent for this study for screening. Assessments performed at outside facilities or on another NIH protocol within the timeframes below may also be used to determine eligibility once a patient has signed the consent.

- **Pathological confirmation:** Patients must have histopathological documentation of prostate cancer prior to enrollment. Note: If no pathologic specimen is available, a clinical course consistent with prostate cancer is acceptable.
- **Within 8 weeks** of study entry: ECG, laboratory tests (CBC with differential and platelet count, hepatic panel, acute care panel, mineral panel, PT/PTT, serum PSA), history and physical examination with documentation of weight, and ECOG performance status.

## 2.3 REGISTRATION PROCEDURES

Registration will be a two-part process as patients are screened on this protocol. Authorized staff must register an eligible candidate with NCI Central Registration Office (CRO) within 24 hours of signing consent. To initially register a subject after the participant has signed the consent, complete the top portion the registration Eligibility Checklist from the website (<http://home.ccr.cancer.gov/intra/eligibility/welcome.htm>) indicating that the patient is being registered for screening and send via encrypted email to: NCI Central Registration Office [[contact]](mailto:[contact]). Once eligibility is confirmed after completion of screening studies, complete the remainder of the form which is the eligibility checklist,

Abbreviated Title: Enzalutamide Formulation PK  
Version Date: 03.11.2020

indicating that the patient is being registered for treatment and email the completed registration checklist to the CRO at NCI Central Registration Office [[contact]](mailto:[contact]). After confirmation of eligibility at Central Registration Office, CRO staff will call pharmacy to advise them of the acceptance of the patient on the protocol prior to the release of any investigational agents. Verification of Registration will be forwarded electronically via e-mail to the research team. A recorder is available during non-working hours.

Subjects that do not meet screening criteria should be removed from the study following the procedure in section 3.5.2.

### 2.3.1 Treatment Assignment and Randomization/Stratification Procedures

#### Cohorts

Single Cohort study

Number	Name	Description
1	Prostate Cancer	Patients with Prostate Cancer

[figure not shown]
#### Arms

Letter	Name	Description
A	Sequence AB	Enzalutamide capsule (Treatment A) followed by enzalutamide liquid (Treatment B)
B	Sequence BA	Enzalutamide liquid (Treatment B) followed by enzalutamide capsule (Treatment A)

#### Randomization and Arm Assignment

Period 1	Minimum 42-day washout	Period 2
Arm A Single dose of 4x40 mg liquid-filled capsules, fasted (n = 6-7)		Arm B Single dose of 4x40 mg liquid-filled capsules, fasted (n = 6-7)

Abbreviated Title: Enzalutamide Formulation PK  
Version Date: 03.11.2020

Patients will be randomized on a 1:1 basis between arms A and B.

The randomization will be performed by the NCI Central Registration Office at the time of enrollment.

## 2.4 BASELINE EVALUATION

- History and physical examination within 17 days of treatment initiation (for medical record only).
- Laboratory studies (Tests completed at screening may be omitted if performed *within 17 days* of treatment initiation): **CBC with differential** and platelet count, **PT/PTT**, and **Acute care panel** (Serum sodium, Potassium test, Serum chloride, CO2, Creatinine, Glucose test, BUN); **Mineral panel** (Albumin, Calcium, Magnesium, Phosphorous – serum); **Hepatic Panel** (Alkaline phosphatase, ALT, AST, direct and total bilirubin); Gamma-GT, LDH, total cholesterol, total protein, Serum PSA, uric acid,
- Urinalysis
- Baseline ECG (within 17 days of treatment initiation)
- Vital signs including weight and height

## 3 STUDY IMPLEMENTATION

### 3.1 STUDY DESIGN

This is a randomized, open-label, single-dose, 2-way crossover, pilot bioavailability trial evaluating two oral formulations of enzalutamide. All men (n=12-14) enrolled in the trial will receive oral enzalutamide in two formulations: Treatment A will be the standard liquid-filled, soft gelatin capsule (reference) formulation; Treatment B will be the liquid formulation (test product). Subjects will be randomized in Period 1 to one of two sequences: AB or BA. Following a minimum 42-day washout period, subjects will be crossed over in Period 2 to receive the treatment that they did not receive in Period 1. Blood samples will be collected for pharmacokinetic analysis.

Subjects are admitted to the Clinical Center on Day 1 (for the first 24-hours of PK sampling) and will take a single 160mg dose of enzalutamide. They are to return to the Clinical Center on Day 3 for the 48h, on Day 8 for the 168h, and Day 42 for the post-dose blood draws. After an appropriate washout period (at least 42 days), subjects will be crossed over in Period 2 to receive the treatment that they did not receive in Period 1. Subjects will be re-admitted to the Clinical Center to receive the study drug and blood samples will be drawn as described above on Days 1, 3, 8, and 42. Drug Administration

*Abbreviated Title: Enzalutamide Formulation PK*  
*Version Date: 03.11.2020*

### **3.2 DRUG ADMINISTRATION**

Enzalutamide will be administered under the following fasting conditions (no caloric intake for 2 hours before dosing and 2 hours after dosing).

Subjects will be randomized in Period 1 to one of two sequences: AB or BA. Subjects are admitted to the Clinical Center on Day 1 (for the first 24-hours of PK sampling) and will take a single 160mg dose of an oral enzalutamide formulation. After an appropriate washout period (at least 42 days), subjects will be crossed over in Period 2 to receive the treatment that they did not receive in Period 1. Subjects will be re-admitted to the Clinical Center to take another 160mg dose of an oral enzalutamide formulation.

Enzalutamide will be administered at approximately 0800 hours with ambient temperature water to a total volume of about 240 mL. When the liquid formulation is administered, the subject will administer the liquid directly from the oral syringe into the mouth and will swallow. Following administration of the liquid dose, a small volume of water (e.g. 3-7 mLs) may be drawn into the syringe and then the contents will be administered orally to the subject. This technique to “rinse” the syringe is intended to reduce the residual enzalutamide remaining in the oral syringe to ensure the complete dose is administered. This will be followed by approximately 240 mL water. When the capsule formulation is administered, capsules must be swallowed whole without breaking, crushing, or chewing with approximately 240 mL water. Subjects are required to refrain from drinking beverages other than water or eating for 2 hours after dosing. Subjects may resume their normal meals 2 hours after dosing.

Abbreviated Title: Enzalutamide Formulation PK  
Version Date: 03.11.2020

### 3.3 STUDY CALENDAR

Procedure	Screening	Baseline	Period 1					Period 2				
			Day 1	Day 2	Day 3	Day 8	Day 42	Day 1	Day 2	Day 3	Day 8	Day 42
Confirmation of diagnosis	X	X										
History and PE	X	X	X g				X	X d				X
Vital signs	X	X	X			X	X	X d				X
Performance Score	X	X					X	X d				X
Labs	X a	X b	X f				X	X d				X
Urinalysis	X	X					X	X d				X
ECG	X	X					X	X d				X
PK c	X	X	X	X	X	X	X	X	X	X	X	X
Adverse Events			X	X	X	X	X	X	X	X	X	X
Concomitant Medications			X			X	X	X d			X	X
Questionnaire			X e					X e				

aFor screening labs see Section 2.2

bFor baseline labs see Section 2.4;

cSee Section 5.1 for complete details.

dWith the exception of PK and adverse events, all assessments and labs on Period 2 Day 1 do not need to be repeated if within 8 days of Period 1 Day 42.

eSubjects will be given a questionnaire (see APPENDIX B) to complete following the administration of the liquid (test) formulation to assess the tolerability. The questionnaire is only completed on the day the liquid formulation is administered. It is not necessary to complete the questionnaire on the day the capsule formulation is administered.

fLabs do not need to be repeated if they were completed at screening/baseline within 17 days of of period 1 day 1.

gH&P may be performed within 17 days of treatment initiation.

*Abbreviated Title: Enzalutamide Formulation PK*  
*Version Date: 03.11.2020*

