#### **1.1.2 Secondary Objective**

- To evaluate the safety and tolerability of two oral formulations of enzalutamide following a single 160 mg dose in male subjects with prostate cancer.

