#### 10.1.6 Tolerability Assessment

To date, there is no available information on the palatability of the liquid enzalutamide preparation. Therefore, a brief tolerability assessment will be completed by each participant. Following the administration of the liquid (test) formulation, participants will be asked to complete [APPENDIX B](#)

Abbreviated Title: Enzalutamide Formulation PK  
Version Date: 03.11.2020

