### **13 APPENDIX B: TOLERABILITY ASSESSMENT OF LIQUID (TEST) ENZALUTAMIDE FORMULATION**

The following questions refer to the liquid enzalutamide formulation you took.

1. Did you complete taking the liquid enzalutamide formulation? (circle one)

yes                      no

If no, why did you not complete taking the medication?

---

2. Please rate the overall taste of the liquid enzalutamide formulation. (circle one)

bad                      almost acceptable                      acceptable                      good

3. Which of the following best describes the taste of the liquid enzalutamide formulation? (circle one)

sweet                      salty                      bitter                      other (please describe below)

---

4. Did you encounter any problems with the use of this liquid formulation?

yes                      no

If yes, please describe what problems you encountered:

---

5. In your opinion, would the liquid formulation be an acceptable way of taking enzalutamide if you had difficulty swallowing? (circle one)

yes                      no

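### The dose-completion and problem questions are asked only after the liquid, so those answers have no capsule counterpart and the extra prompt may inflate mild adverse-event counts for the liquid

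*Combined protocol and SAP*

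**What the plan says.** Section 1.1.2 states the secondary objective: "To evaluate the safety and tolerability of two oral formulations of enzalutamide following a single 160 mg dose". Section 3.1 describes the trial: "This is a randomized, open-label, single-dose, 2-way crossover, pilot bioavailability trial evaluating two oral formulations of enzalutamide". Every man takes both products, and both he and the staff know which one he has taken.

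Footnote e of the Study Calendar (section 3.3) gives the purpose of the Appendix B form as assessing tolerability, and restricts it: "The questionnaire is only completed on the day the liquid formulation is administered". It then adds: "It is not necessary to complete the questionnaire on the day the capsule formulation is administered". Section 10.1.6 gives the reason, "To date, there is no available information on the palatability of the liquid enzalutamide preparation", and sets the same timing: "Following the administration of the liquid (test) formulation, participants will be asked to complete".

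Appendix B has five questions: whether the dose was completed and, if not, why (1); overall taste (2); type of taste (3); any problems, with free text (4); and whether the liquid would be acceptable to someone with difficulty swallowing (5). Question 4 reads: "Did you encounter any problems with the use of this liquid formulation".

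The same calendar schedules adverse events on Days 1, 2, 3, 8 and 42 of both periods. Section 8.4.3 reports episodes and grades of nausea and vomiting by formulation and tests grade 3 vomiting. Section 8.4.4 tabulates toxicity counts, with nausea and vomiting as the main toxicity. Neither section mentions the form.

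**The concern.** A tolerability objective that names two products needs the same question asked of each. Questions 2 and 3 concern the taste of the liquid and question 5 its acceptability, so these belong to the liquid. Questions 1 and 4 do not: a man can fail to finish four capsules, or have trouble with them, as readily as with a syringe of liquid. Sections 1.2.3 and the Précis themselves mention the number of capsules and difficulty in swallowing as reasons for the study. Yet the capsule day has no matching question.

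Two things are at stake. First, a count of men who report problems with the liquid will have no capsule count beside it. Second, a written invitation to report problems on one of the two dosing days could bring out mild complaints that would go unmentioned on the other. If such complaints are then recorded as adverse events, the counts by formulation in section 8.4.4 would tilt against the liquid. Section 9.5 already names local irritation and aspiration as risks that may be greater with the liquid, so an observed excess of mild local complaints could not be separated from the extra prompting.

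**Working it through.** The plan gives no figure for questionnaire answers or for the frequency of minor problems, so there is nothing of its own to reproduce on this point. Its total of 12 men (section 8.2) was chosen for the AUC comparison and is used below only as a head count.

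**Step 1: what is asked after each product.**

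| Item | After liquid | After capsule | Source |
|---|---|---|---|
| Adverse events, Days 1, 2, 3, 8, 42 | Yes | Yes | 3.3 |
| Admission for the first 24 hours | Yes | Yes | 3.1, 3.2 |
| Dose completed, and if not why (question 1) | Yes | No | 3.3 footnote e, Appendix B |
| Any problems, free text (question 4) | Yes | No | 3.3 footnote e, Appendix B |
| Taste (2, 3) and acceptability (5) | Yes | Not applicable | Appendix B |

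Footnote d, which lets some Period 2 Day 1 assessments be skipped, exempts adverse events. The adverse-event schedule is therefore the same for both products, and the imbalance lies in questions 1 and 4 alone.

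**Step 2: can the imbalance reach the planned analysis?** The documents do not say whether a problem written under question 4 is also recorded as an adverse event, whether events first learned from the form are marked, or how adverse events are elicited after either product. Section 6.1 follows adverse events of any severity, so a mild event written on the form could enter the record. Such a route is possible, but no passage establishes it. Mild events in the 8.4.4 counts are the most exposed; grade 3 vomiting in an admitted man is the least.

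**Step 3: illustration of size.** All rates here are assumptions; none comes from the documents. Let the true proportion of men with a minor problem be p for both products, and let the probability that a problem is captured be c_L after the liquid and c_C after the capsule. Then:

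apparent excess for the liquid = p × (c_L − c_C)

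With p = 0.30, c_L = 0.90 and c_C from 0.30 to 0.70, in 12 men:

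- liquid: 12 × 0.30 × 0.90 = 3.24 reports
- capsule: 12 × 0.30 × 0.30 = 1.08 to 12 × 0.30 × 0.70 = 2.52 reports
- excess: 3.24 − 2.52 = 0.72 to 3.24 − 1.08 = 2.16 men; divided by 12, this is 6 to 18 percentage points with no true difference.

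The result moves with the assumptions. Keeping c_L = 0.90:

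| p | c_C = 0.60 | c_C = 0.30 |
|---|---|---|
| 0.20 | 6 points | 12 points |
| 0.30 | 9 points | 18 points |
| 0.50 | 15 points | 30 points |

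If c_L = c_C, the excess is 0 whatever p is. These figures describe minor problems in general and do not estimate bias in nausea or vomiting.

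**The case against.** The strongest reply is that the form was never meant for comparison. Section 10.1.6 presents it as a check on palatability because nothing is known about the taste of the liquid, whereas the capsule is the marketed product. A descriptive form for the new product alone is a defensible choice in a pilot of 12 to 14 men. The comparison that is planned uses adverse events, which are collected on the same days and in the same setting after both products. Appendix B does not mention nausea or vomiting, and question 4 may draw remarks on handling or taste that are not adverse events at all.

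Most of this stands, and it limits the point. A reader might infer that the two formulations cannot be compared fairly; the equal adverse-event schedule and the content of section 8.4.3 do not support that. A reader might also infer that capsule problems are left to spontaneous report, or that entries on the form will become adverse events; the documents say neither. Nor is it a fault that a convenience advantage could not be shown, since convenience is background rationale and is neither an objective nor an endpoint.

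The reply does not dispose of questions 1 and 4. Footnote e gives the purpose as tolerability, Appendix B carries that word in its title, and the secondary objective applies it to both products. Those two questions go beyond taste and have a direct capsule equivalent.

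**Conclusion.** The point holds in a limited form. Answers on dose completion and on problems cannot be compared between formulations, because they are collected for one of them only; this follows from the text and needs no assumption. That the extra prompt inflates mild adverse-event counts for the liquid in section 8.4.4 is a risk, and whether it occurs depends on a recording practice that the documents leave open. The planned nausea and vomiting comparison rests on equally scheduled adverse events, and the formal test of grade 3 vomiting is little exposed. The size of any bias is unknown: the 6 to 18 points depend wholly on the assumed problem and capture rates. The primary AUC endpoint and the sample size are unaffected. The change is worth making because it is cheap and because capsule-day answers that were never asked for cannot be recovered reliably later.

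**What to change.** Amend footnote e of section 3.3, section 10.1.6 and Appendix B as follows:

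- Have questions 1 and 4 completed after each dose in both periods, worded as *the formulation you took today*.
- Keep taste questions 2 and 3 and acceptability question 5 for the liquid day only.
- State in section 8.4.3 or 8.4.4 that questions 1 and 4 are reported descriptively by formulation as within-man pairs.
- Flag any adverse event first learned from the form, so that the counts in section 8.4.4 can be read with and without such events.

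The cost is one extra short form per man, on a day when he is already admitted, and slightly more data entry. No visit, blood sample or additional patient is needed.

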### **3.4 COMPENSATION**

Study participants will be compensated for each blood sample collected for PK analysis as follows:

- \$20 for the 1st pre-dose (0 hour) PK sample
- \$20 for the 2nd (30 minutes post dose) PK sample
- \$20 for the 3rd (1 hour post dose) PK sample
- \$20 for the 4th (2 hours post dose) PK sample
- \$20 for the 5th (4 hours post dose) PK sample
- \$20 for the 6th (8 hours post dose) PK sample
- \$20 for the 7th (24 hours post dose) PK sample
- \$20 for the 8th (48 hours post dose) PK sample
- \$20 for the 9th (168 hours post dose) PK sample
- \$20 for the 10th (Day 42 post dose) PK sample

All remuneration will be directed to be paid to the participant via check through standard compensation procedures. These funds are intended to compensate for time away from work that is required to participate in this study. As we intend to recruit from the local metropolitan region, we will not provide remuneration for meals, lodging or transportation. If a participant withdraws from study, no future compensation will be made, but prior compensation will not be revoked.

Subjects will not receive direct benefit from their study participation in this protocol.

Subjects will only be compensated if samples are collected solely for research purposes.

If subjects return to clinic solely for any clinical/non-research reasons, subjects will not be reimbursed.

### **3.5 CRITERIA FOR REMOVAL FROM PROTOCOL THERAPY AND OFF STUDY CRITERIA**

#### **3.5.1 Criteria for removal from protocol therapy**

- Completion of protocol therapy
- Participant requests to be withdraw from active therapy
- Unacceptable Toxicity as determined by the investigator
- Investigator discretion

#### **3.5.2 Off-Study Criteria**

- Completed study follow-up period
- Participant requests to be withdrawn from study
- Loss of capacity to render informed consent
- Death
- Screen failure

*Abbreviated Title: Enzalutamide Formulation PK*  
*Version Date: 03.11.2020*

### 3.5.3 Off Protocol Therapy and Off-Study Procedure

Authorized staff must notify Central Registration Office (CRO) when a subject is taken off protocol therapy and when a subject is taken off-study. A Participant Status Updates Form from the web site (<http://home.ccr.cancer.gov/intra/eligibility/welcome.htm>) main page must be completed and sent via encrypted email to: NCI Central Registration Office [[contact]](mailto:[contact]).

## 4 CONCOMITANT MEDICATIONS/MEASURES

Patients may be on concomitant drugs to prevent bone loss, including calcium, vitamin D, bisphosphonates and denosumab.

Other supportive care with blood components, antibiotics, analgesics, general medical therapy, etc., will be delivered as required.

### 4.1 GENERAL GUIDELINES

All medications (other than study drug) and significant non-drug therapies (including physical therapy and blood transfusions) taken within 28 days of starting study treatment through the follow up visit should be reported on the CRF.

While patients are on protocol treatment, all medications required for the health of the patient are allowed with the following exception: concomitant use of herbal supplements.

### 4.2 SEIZURE THRESHOLD LOWERING DRUGS

Use caution when coadministering medications which may lower the seizure threshold.

### 4.3 CYTOCHROME P450 AND P-GLYCOPROTEIN

- Co-administration of enzalutamide with strong or moderate CYP2C8 inducers (e.g., rifampin) or inhibitors may alter the plasma exposure of enzalutamide and are not allowed while on study.
- Co-administration of enzalutamide with strong CYP3A4 inducers (e.g., carbamazepine, phenobarbital, phenytoin, rifabutin, rifampin, rifapentine) or inhibitor may alter the plasma exposure of enzalutamide and are not allow while on study. Selection of a concomitant medication with no or minimal CYP3A4 induction potential is recommended.
- Moderate CYP3A4 inducers (e.g., bosentan, efavirenz, etravirine, modafinil, nafcillin) and St. John's Wort may also reduce the plasma exposure of enzalutamide and should be avoided if possible.
- Concomitant use of enzalutamide with narrow therapeutic index drugs that are metabolized by CYP3A4 (e.g., alfentanil, cyclosporine, dihydroergotamine, ergotamine, fentanyl, pimozide, quinidine, sirolimus and tacrolimus), CYP2C9 (e.g., phenytoin, warfarin), or CYP2C19 (voriconazole) should be avoided, as enzalutamide may decrease their exposure.
- Grapefruit, Seville oranges, and starfruit affect P450 and PgP activity. Concomitant use should be avoided.

Abbreviated Title: Enzalutamide Formulation PK  
Version Date: 03.11.2020

